The randomization list with treatment assignments corresponding to randomization numbers will be generated by the study statistician not involved in screening or enrollment of study subjects. The research pharmacist, also not involved in screening or enrollment, will receive the list and keep it concealed. For each infant enrolled, the research staff will obtain the treatment assignment corresponding to the infant’s randomization number from the research pharmacist by phone thus eliminating allocation bias⁶⁸.

1.1.4.8. Blinding:

All enrolled infants will receive active medication; only the research staff and pharmacist will be aware of the infants’ assigned group. Study medication will be reconstituted by research staff in a designated private space in the NICU. The clinical caregivers and subjects will be blinded to dose and dilution, although an experienced clinical caregiver may be able to guess the dose and dilution. Research staff monitoring the enrolled infants during study intervention will collect objective data thus minimizing bias. It is not possible to blind nebulizers as they are of very different configurations and covering them will interfere with monitoring during clinical care. Infants will remain on their allocated nebulizer device for the duration of the study.

1.1.4.9. Clinical Care of Enrolled Infants:

The attending neonatologist and clinical team will make all decisions for initiation of NIV support and need for intubation and/or intratracheal surfactant instillation. Consensus guidelines have been agreed upon by clinical staff based on previously published studies for consistency^{7,33,34,69-74}.

Suggested initial and maximum settings for NIV support are provided although clinicians may individualize care (Table 11)^{33,34,74}. Escalation of NIV will be recommended for increasing FiO₂ (>10% from baseline), partial pressure of CO₂ (PCO₂, >10 mmHg from baseline), or clinical respiratory distress. Weaning will be recommended for SpO₂ and PCO₂ maintained at 90-95% and <65 mmHg respectively for 4 hours in the absence of significant clinical signs of respiratory distress³⁴.

Table 11: Suggested initial and maximum settings for NIV support

Settings	NIPPV		NCPAP		HFNC	
	Initial	Max	Initial	Max	Initial	Max
rate bpm	10	40				
PIP (cm H ₂ O)	10 above PEEP	18				
PEEP (cm H ₂ O)	5-6	8	5-6	8		

FiO2 % to maintain SpO2	90-95%	90-95%	90-95%	90-95%	90-95%	90-95%
Ti Seconds	0.3-0.5	0.3-0.5				
Flow LPM	8-12	8-12	8-12	8-12	2-3	5-6

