In our unit, infants ≤ 32 weeks GA with RDS being treated with NIV receive *caffeine* shortly after starting NIV as recommended/reported in the literature^{7,74}. Enrolled infants will receive the 1st dose of caffeine prior to study intervention as standard clinical care in this study. This will prevent confounding of assessment of efficacy of study intervention both within and between subjects by caffeine effect. Caffeine therapy will consist of an intravenous loading dose of 20 mg/kg caffeine citrate/kg body weight followed by a daily maintenance dose of 5 mg/kg; duration of treatment will be determined by the clinical team.

Recommended criteria for intubation will be same as defined under Exit criteria (Section 3.6.5). If in an enrolled infant respiratory distress progresses and criteria for intubation are met prior to the institution of nebulized surfactant, the infant will exit the study and rescue therapy will be instituted immediately. *Recommended criteria for adjustments to ventilator settings* on conventional and high frequency ventilation include maintaining PaO₂ 50 to 70 mmHg, or oxygen saturation 90% - 95%, and PaCO₂ <65 mmHg.

Infants who are enrolled in the study and subsequently require intubation may receive *intratracheally instilled surfactant* at the discretion of the clinical team. It is not necessary to wait 6 hours from last dose of AS to administer the first dose of intratracheal surfactant if other clinical criteria are met⁷⁵. *Criteria for subsequent clinical intratracheal surfactant doses* (drawn from a clinical stock of Survanta) will include need for MV with FiO₂ >0.30 and mean airway pressure >7 cm H₂O for ≥ 20 min at ≥ 6 hours from last dose^{69,76}.

It will be recommended that extubation be attempted within 24 hours after the infant meets all of the following criteria: PaCO₂ <65 mm Hg, pH >7.20, SpO₂ 90-95% with an FiO₂ < 0.50, mean airway pressure <10 cm of water, ventilator rate < 20 breaths per minute, an amplitude of less than twice the mean airway pressure if high-frequency ventilation is being used, and hemodynamic stability⁷⁵.

All PT neonates with respiratory distress requiring NIV receive a *chest radiograph* (CXR) as standard clinical care; a CXR is not mandatory prior to enrollment for this study. *Echocardiography* and *cranial sonography*, will be performed at the discretion of the clinical team based on infants GA and clinical status.

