For PT infants with RDS to have the best outcome it is essential that they have *optimal supportive care*, including delivery room care, maintenance of normal body temperature, proper fluid management, nutritional support, circulatory support to maintain blood pressure & tissue perfusion, and skin-to-skin contact and kangaroo care⁷. Clinical protocols in place for the care of preterm infants in our unit will be followed.

1.1.4.10. Monitoring During & After Aerosol Administration:

Every attempt will be made to administer AS with the infant in stable condition, with heart rate >120 bpm, and oxygen saturation (SpO₂) >85%. Prior to or concurrent with enrollment, capillary/arterial blood gas (CBG/ABG) analysis, vital signs including pulse oximetry (SpO₂), respiratory support & receipt of medications such as caffeine, pressors or sedation will be recorded. Newborn respiratory distress score used in the Acute Care of At-Risk Newborns (ACoRN) program (adapted from Downes) will be used to objectively evaluate changes in respiratory distress during study intervention^{77,78} (Appendix VII [Table A5])). Severity of illness will be determined using the CRIB (Clinical Risk Index for Babies) score^{79,80} (Appendix VII [Table A6])).

Adverse events (AEs) during study aerosol administration will be recorded including: desaturations, apnea, bradycardia, tachycardia, air leaks, need for resuscitation, occurrence of coughing/gagging, surfactant reflux from the nose/mouth, need for positive pressure inflations, residual surfactant in nasal prongs or nebulizer chamber, and rainout in the ventilator tubing (Appendix VII [Tables A8-A9])). We will take pictures of components of the ventilator circuit without taking a picture of the subject – but this will not be mandatory. 60 \pm 30 minutes after end of nebulization, a CBG/ABG will be obtained and SpO₂ values noted. It will be requested that clinical team make no changes to respiratory support from the start of aerosol till the CBG/ABG 60 \pm 30 minutes after end of nebulization has been obtained. However, if for patient well-being these changes are deemed necessary during this time by the clinical team, a note will be made in the research records.

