A number of secondary outcomes will be assessed using the same methodology. Vital signs, SpO₂, FiO₂, NIV parameters (pressure, rate, flow) and ABG/CBG components (pH, PO₂, PCO₂) will be evaluated before and after study intervention (paired *t*-test) and over time (Longitudinal data analysis). Other secondary outcomes include change in surfactant activity in gastric aspirates, changes in cerebral oxygenation, diagnosis of PDA, need for blood transfusions, postnatal growth, duration of respiratory support, length of hospital stay, and incidence of complications of prematurity including IVH, sepsis, NEC, BPD, pneumonia, ROP, and death. We will describe and compare primary and secondary outcome data overall and by dosing schedule, and in three pre-planned subgroup analyses – by dose regardless of dilution (100 mg/kg vs 200 mg/kg), GA group stratum and nebulizer type, recognizing that we may observe trends of differences between groups without having power to determine statistical significance. We will report dichotomous secondary outcome data as proportions and compare the groups using χ^2 and nonparametric tests. We will report secondary continuous outcome data as mean (SD) for normally distributed data and median (interquartile range [IQR]) for skewed data, and will compare the groups by using parametric (*t*-test, ANOVA) and nonparametric tests (Mann-Whitney U test, Wilcoxon's test) as appropriate. Pairwise group comparisons of the four dosing schedule groups will also be performed, although we may lack power to detect significant differences. In a final posthoc analysis, we will compare infants who received intubation within 72 hours to those who did not to understand risk factors for intubation and their modification by study intervention. This analysis will be presented for the entire group and by dosing schedule group. In *adjusted analyses*, dosing schedule, GA group, nebulizer type, mode of NIV, antenatal steroids, and presence of PDA or IVH will be included as covariates recognizing that these analyses are exploratory and need to be interpreted cautiously. We will consider a p value of <0.05 for statistical significance. Mock tables for the planned analyses are presented in Appendix IX.

Recommendations for statistical analyses by the Data Monitoring Committee (DMC) during the conduct of the trial:

1. Additional factors associated with intubation in enrolled infants – clinical team, time of day/shift, clinical variables (e.g. sepsis, NEC)

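### SpO2, FiO2 and blood-gas PO2 are analysed one at a time: no planned measure combines saturation with FiO2, and no rule keeps capillary and arterial PO2 apart

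*Combined protocol and SAP*

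**What the plan says.** Section 1.1.12, in its paragraph on secondary outcomes, lists "Vital signs, SpO₂, FiO₂, NIV parameters (pressure, rate, flow") and then the gases: "ABG/CBG components (pH, PO₂, PCO₂) will be evaluated before and after study intervention". Each is to have a paired t-test and a longitudinal analysis. The same paragraph adds a comparison across groups: "We will describe and compare primary and secondary outcome data overall and by dosing schedule". The Aim 1 plan in 1.1.12 also runs paired tests on SpO2, PCO2 and cerebral oxygenation. It repeats them between intubated and non-intubated infants, and before against after intubation. FiO2 is not named there, nor in the first item of Secondary Efficacy Outcomes (1.1.8).

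Clinical Care of Enrolled Infants (1.1.4.9) treats saturation as a target. Table 11 has a row "FiO2 % to maintain SpO2" with 90-95% for every mode. The text adds: "Weaning will be recommended for SpO₂ and PCO₂ maintained at 90-95% and <65 mmHg respectively for 4 hours". For ventilated infants the recommendation is "maintaining PaO₂ 50 to 70 mmHg, or oxygen saturation 90% - 95"%.

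Monitoring (1.1.4.10) allows either type of gas before dosing ("capillary/arterial blood gas (CBG/ABG) analysis, vital signs including pulse oximetry") and again 60±30 minutes after nebulization ends ("a CBG/ABG will be obtained and SpO₂ values noted"). It asks the clinical team to leave respiratory support alone from the start of aerosol until that second gas. Departures are permitted for the infant's well-being and are to be noted.

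**The concern.** A variable that clinicians steer towards a target is a weak outcome by itself. If a schedule improves oxygenation and FiO2 is lowered in response, the gain shows in FiO2 and SpO2 stays in its band. If FiO2 is not touched, the gain shows in SpO2. In between, it is split over two tests, each of which sees only part of it. The exit criteria (1.1.6) already read the two together, as the FiO2 needed to keep saturation in the band, but the analysis plan does not.

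For PO2 the difficulty is comparability within an infant. Capillary and arterial values may not lie on one scale. A paired test takes each infant as its own control, and that fails if the sample type changes between the two times. At stake is the reading of the short-term physiological response: a null SpO2 result could be taken as no effect, and a PO2 change could be taken as an effect.

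**Working it through.** **Plan's own figure.** There is none to reproduce. The documents give no SD, effect size or power for SpO2, FiO2 or PO2. The precision and power tables (Tables 12 and 13) concern intubation within 72 hours and do not depend on this point.

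**1. SpO2 and FiO2, simplest case (assumed values).** Two schedules both sit at SpO2 93%, with FiO2 0.30 and 0.40.
- Difference in SpO2: 93 - 93 = 0.
- Difference in FiO2: 0.10.
- SpO2/FiO2: 93/0.30 = 310 against 93/0.40 = 232.5.

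Here the ratio only restates the FiO2 difference, which the plan does test. The ratio adds something when both variables move.

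**2. Both variables move (illustrative simulation; every input is an assumption except 30 per schedule and alpha 0.05).** The true difference between two schedules is worth 6 FiO2 points, SD 10. One FiO2 point equals 0.5 SpO2 point. Measurement noise has SD 3 for SpO2 and 2 for FiO2. Baseline is SpO2 93% and FiO2 40%; for the ratio, SpO2 is capped at 100% and FiO2 cannot fall below 21%. The test is a two-sided t-test. If titration absorbs a share c of the gain, the expected differences are 0.5 × (1 - c) × 6 SpO2 points and c × 6 FiO2 points.

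| Share absorbed c | Expected SpO2 difference | Expected FiO2 difference | Power, SpO2 | Power, FiO2 | Power, SpO2/FiO2 |
|---|---|---|---|---|---|
| 0 | 3.0 | 0 | 50% | 5% | 28% |
| 0.25 | 2.25 | 1.5 | 43% | 44% | 50% |
| 0.50 | 1.5 | 3.0 | 31% | 56% | 55% |
| 0.75 | 0.75 | 4.5 | 14% | 60% | 57% |
| 1 | 0 | 6.0 | 5% | 61% | 57% |

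Each single variable falls to the 5% error rate at one extreme. The ratio does not, although it is not always the most powerful of the three.

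**3. PO2, mean paired change.** Shift = net share moving from arterial to capillary × offset. With an assumed net 30% and capillary PO2 assumed 5 to 20 mmHg lower: 0.30 × 5 = 1.5 and 0.30 × 20 = 6, so -1.5 to -6 mmHg with no treatment effect. If equal shares move in each direction, the mean shift is 0.

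**4. PO2, noise.** Let a share q of samples be capillary at each time, independently, with offset D. The extra variance of a change is 2q(1 - q)D². Assume q = 0.5 and an SD of change of 15 mmHg (variance 225):
- D = 5: extra 12.5; SD = √237.5 = 15.4.
- D = 10: extra 50; SD = √275 = 16.6.
- D = 20: extra 200; SD = √425 = 20.6.

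For the same precision, the number of infants would rise by a factor of 237.5/225 = 1.06 to 425/225 = 1.89.

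**5. PO2 between schedules.** If every schedule has the same net move, each mean shifts by the same amount and the difference between schedules is 0. Bias would need the mix of sample types to differ by schedule.

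**The case against.** A reader might infer that neither SpO2 nor PO2 can measure a schedule's effect on oxygenation, and that SpO2 should be kept only as a safety variable. The documents do not support that.

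- FiO2 stands next to SpO2 in the same sentence of 1.1.12, with the same tests. When saturation is held by titration, FiO2 carries the signal.
- During the hold in 1.1.4.10, SpO2 is free to respond. That is the window of the first secondary outcome in 1.1.8, and the natural one for the before/after test.
- The Table 11 settings are suggestions that clinicians may individualize. Entry does not require FiO2 of 25% or more if the pressure or flow criterion is met, and in room air FiO2 cannot be lowered further.
- Sample type has no stated link to schedule. Clinical caregivers are to be blinded to dose and dilution (1.1.4.8), although the protocol accepts that some may guess.
- The outcomes that Aim 2 lists for choosing a schedule include neither SpO2 nor PO2. Cerebral oximetry and duration of supplemental oxygen are also planned.
- The plan is silent on pooling sample types rather than committed to it, and the forms and mock tables in Appendices VIII and IX are not available here.

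Most of this stands and sets the limits of the point. It does not remove it. The hold is a request with exceptions, no analysis rule uses the recorded exceptions, and it ends at the post-dose gas while monitoring runs to 72 hours. The hold also lasts longer for larger volumes. Total volumes are 8, 12, 16 and 24 ml/kg for Schedules I to IV. At the MiniHeart's 8 ml/h, a 1 kg infant needs 1, 1.5, 2 and 3 hours, which leaves more time for exceptions. The comparison before and after intubation, where FiO2 may well change, names SpO2 without FiO2.

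**Conclusion.** The point holds in limited form. Once FiO2 is adjusted, a test of SpO2 alone is drawn towards no difference. FiO2 is analysed too, but nothing planned reads the two together. A paired PO2 test run as written can shift with sample type: by -1.5 to -6 mmHg under the assumed 30% net move and 5-20 mmHg offset, and by nothing on average if moves balance. Neither assumption comes from the documents. Between randomized schedules the expected harm is lost precision rather than bias. The simulated power figures show a pattern and do not predict this trial's power. Removing SpO2 as a listed secondary outcome is not justified. These outcomes are secondary and exploratory, the primary outcome is untouched, and the change is desirable rather than essential.

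**What to change.** In 1.1.12:

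1. Add SpO2/FiO2, adjusted for baseline, as an oxygenation measure in the before/after, longitudinal and between-schedule analyses. Keep SpO2 and FiO2 as listed.
2. Restrict the paired PO2 test to infants with the same sample type at both times, with arterial-arterial pairs as the main analysis.
3. Include sample type as a covariate for pH and PCO2.
4. Add a sensitivity analysis for infants whose respiratory support was noted as changed during the hold.

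The cost is SAP wording, a variable derived from data already recorded, and a little more analysis. Sample type must be kept as a data field with each gas. Fewer infants will contribute to the PO2 result; the documents do not show how many. The ratio does not reflect pressure or flow, so the planned analyses of NIV parameters should stay beside it.

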Nasal trauma will be scored prior to AS, at end of AS and at 24 hours after AS^{53,81} (Appendix VII [Table A7])). At each time point, the nasal prongs will be briefly slid out of the nares and scores assigned for redness, bleeding, ulceration, or skin breakdown (Nasal Trauma Score) by research staff. In addition at the conclusion of the study intervention, the bedside nurse and respiratory therapist will complete a *Feasibility Questionnaire* to determine impact of study intervention on clinical care (Appendix VIII).

Ventilator parameters and vital signs will be monitored every 15 min during administration of aerosol, 30 min after completion of aerosol, every hourly till 4 hours and every 4 to 8 hour till 72h after completion of aerosol. CBG/ABGs are generally followed every 4 to 6 h for the first 24 h of life and every 4 to 12 h for the next 48 h, as clinically indicated and will be recorded. Cerebral oxygenation will be monitored before, during and after AS in all subjects. Demographic and clinical data will be collected prospectively. We will also record respiratory support at 3d, 7d, 14d, 28d and 36 weeks corrected GA; clinical course; need for medications (caffeine, pressors, sedation, indomethacin/ibuprofen, diuretics, postnatal steroids, antibiotics course, blood transfusions); morbidities; outcomes at discharge; and laboratory and imaging results.

1.1.4.11. Cerebral Oximetry Using Near Infrared Spectroscopy (NIRS):

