- ii). Secure cooperation of clinical bedside nurses and respiratory therapists in administering aerosol.
- iii). Identify and randomize a sufficient number of patients within a reasonable study period. This includes ability to identify eligible infants, obtain informed consent, and prepare and deliver aerosolized study medication in the defined time frame.

1.1.7.3. Dose Finding:

We will randomize infants to receive one of 4 fixed dosing schedules. Data collected during this Phase I/II trial will be critical in selecting the optimal dosing schedule for the definitive Phase III trial. Optimal dosing schedule will be determined by preliminary evidence of efficacy, lack of adverse effects, and tolerance by patients and bedside clinical caregivers.

1.1.7.4. Efficacy:

The primary efficacy outcome for this Phase I/II trial is the need for need for intubation and MV within 72 hours of study intervention (treatment failure). This will be compared to a historical control rate of 0.5 for need for intubation in PT infants 24-36 weeks GA undergoing NIV. Treatment failure criteria are defined *a priori* in Section 3.6.5. We chose treatment failure within 72 hours of randomization as our primary efficacy outcome as failure within that time would likely be due to RDS, whereas failure after this time would more likely be due to secondary causes like sepsis, PDA, pneumonia, NEC, IVH, or apnea of prematurity.

1.1.8. Secondary Efficacy Outcomes:

1. CBG/ABG, pulse oximetry, vital signs at 60±30 minutes after end of AS
2. Number of doses of surfactant – aerosolized & intratracheal
3. Respiratory support at 24, 48 & 72 hours, 7 days (D7), D14, D28, 36 weeks corrected GA and Discharge.
4. Pneumothorax, pneumomediastinum or other air leak
5. Changes in cerebral oxygenation as evaluated by NIRS
6. Changes in surfactant activity in gastric aspirates
7. Cumulative duration of NIV and invasive ventilation on D3, D7, D14, D28, 36 weeks CGA and discharge
8. Duration of supplemental oxygen, intensive care, hospital stay
9. Age at start of feeds, feeding progression, age at full enteral feeds
10. Need for blood transfusions
11. Growth parameters at 7 days, 28 days, 36 weeks corrected GA and discharge
12. Morbidities associated with prematurity: PDA, IVH (Grade III-IV), NEC, periventricular leukomalacia, ventriculomegaly, ROP (stage>3 or requiring treatment), and BPD. Two definitions of BPD will be used:

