Analysis plan to address Aim #2: - Determination of Optimal Dilution and Dosage of AS: The optimum dose is one that produces low toxicity while nearly maximizing the biological response⁸⁹. The optimal dosage will be determined by comparing levels of adverse responses, feasibility items and primary and secondary efficacy treatment outcomes (rates of intubation, diagnosis of PDA, need for blood transfusions, postnatal growth, duration of respiratory support, length of hospital stay, and incidence of complications of prematurity including IVH, sepsis, pneumonia, BPD, NEC, ROP, and death) across the four dosing schedules (Appendix IX, Mock Tables). The optimal dosage/dilution will be the one with the minimum level of adverse responses and highest clinical treatment outcomes.

Analysis plan to address Aim #3 - Short-term efficacy of AS: The primary outcome variable for short-term efficacy is the need for intubation & MV within 72 hours of AS. We will estimate the unconditional probability of benefit for the four dosing schedule groups (I, II, III, IV), the 2 dose groups (100 vs. 200 mg/kg) and the entire study cohort of 120 subjects. We will also compare with reported rates of intubation in historical controls (50%). A special χ^2 test to compare sample proportion with population proportion will be conducted to test the study hypothesis that AS is efficacious. In the comparison analysis, different dosages/dilutions will also be considered as weight using the “optimal” dosage/dilution obtained from Aim #2 as reference. A significantly lower rate of intubation in infants treated with AS in this study as compared to the reported rate of ~0.5 at $p < 0.05$ level (two-sided) will be used as evidence supporting the efficacy of AS. However, it is likely we may not

have power to achieve statistically significant results. Nevertheless these preliminary efficacy data will be crucial in determining outcome measures and effect size for the definitive placebo-controlled Phase III trial.

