2. Performing a survival curve analysis to present timing of intubation in infants who were intubated
3. Control for mode of ventilation at baseline and exploring a GA cutoff at which this intervention may be most beneficial.
4. Detailed caffeine data in relation to AS to be provided
5. DMC requested data for intubation rates in the three GA strata outside this clinical trial setting (as reported in the literature and at Hutzel Women's Hospital by initiating an observational study) as there is no placebo group in this analysis
6. Handling of infants that exited study prior to study intervention
 - a. DMC recommended performing a dual level analysis
 - i. The primary “intent to treat analysis” should include all enrolled subjects.
 - ii. A secondary “experimental analysis” should also be presented that only includes subjects that received study intervention.

REFERENCES:

1. International conference on harmonisation: General Considerations for Clinical Trials. *Fed Regist.* 1997;62(242):66113.
2. Piantadosi S. Clinical trials as experimental designs. In: Balding DJ, Cressie NAC, Fisher NI, et al., eds. *Clinical Trials: A Methodologic Perspective*. 2nd ed. New Jersey: John Wiley & Sons; 2005:127-165.
3. International conference on harmonisation; guidance on statistical principles for clinical trials; availability--FDA. Notice. *Fed Regist.* 1998;63(179):49583-49598.
4. Food, Drug Administration HHS. International Conference on Harmonisation; choice of control group and related issues in clinical trials; availability. Notice. *Fed Regist.* 2001;66(93):24390-24391.

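### The exploratory adjusted analyses put PDA and IVH, the trial's own outcomes with no timing limit, in the same model as dosing schedule, so adjusted schedule effects can be biased

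*Combined protocol and SAP*

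**What the plan says.** The adjusted analyses in Statistical Analyses (1.1.12) name six terms: dosing schedule, GA group, nebulizer type, mode of NIV, antenatal steroids, and PDA or IVH. The sentence closes: "presence of PDA or IVH will be included as covariates recognizing that these analyses are exploratory and need to be interpreted cautiously". It gives no time limit and no IVH grade, and it does not name the dependent variable. The sentence before it describes a post hoc comparison of intubated and non-intubated infants "to understand risk factors for intubation and their modification by study intervention".

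Elsewhere the plan treats PDA and IVH as results of care:

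- Secondary Efficacy Outcomes (1.1.8), item 12, begins "Morbidities associated with prematurity: PDA, IVH (Grade III-IV), NEC".
- The Aim #2 analysis in 1.1.12 selects the dose partly on diagnosis of PDA and on "incidence of complications of prematurity including IVH, sepsis, pneumonia, BPD, NEC, ROP, and death) across the four dosing schedules".
- Efficacy (1.1.7.4) justifies the 72-hour window on the ground that "failure after this time would more likely be due to secondary causes like sepsis, PDA, pneumonia, NEC, IVH, or apnea of prematurity".

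On ascertainment, the Time & Event Table (Table 9) lists no baseline echocardiogram or cranial scan. Clinical Care (1.1.4.9) says these examinations "will be performed at the discretion of the clinical team based on infants GA and clinical status". Monitoring (1.1.4.10) collects "morbidities; outcomes at discharge; and laboratory and imaging results" with no cut-off.

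**The concern.** Randomization makes the four schedules comparable at baseline. Adjusting for pre-dose variables preserves that. Adjusting for something that happens after dosing need not, and there are three ways it can go wrong here:

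1. **Mediator.** If schedule changes PDA/IVH and PDA/IVH changes the risk of intubation, adjustment removes that part of the schedule effect.
2. **Common cause.** If schedule changes PDA/IVH, and unmeasured illness severity drives both PDA/IVH and intubation, adjustment links schedule to severity and can create an effect where none exists.
3. **Reverse order.** If PDA/IVH is diagnosed after intubation and depends on both intubation and schedule, the model conditions on a consequence of its own outcome.

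Surfactant is given within the first 24 hours of life (1.1.4.2) and scans are done when clinical status prompts them, so the plan excludes none of the three. At stake is how the adjusted schedule estimates are read when the Phase III trial is designed.

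**Working it through.** **Plan's own figure.** The plan gives no number for the adjusted model. Its main design figure is 81.8% power per schedule (n = 30, 0.25 against 0.5, two-sided 0.05). The arcsine formula reproduces it: Φ(2·|asin√0.5 − asin√0.25|·√30 − 1.96) = Φ(2.868 − 1.960) = 0.818. No covariate enters, so this figure does not depend on the point.

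**Status of the inputs.** The documents give no PDA or IVH rates or associations. Every input below is assumed. The odds ratios (OR) are exact large-sample fits of logit P(intubation) = a + b·schedule + c·(PDA/IVH), for two schedules of equal size, with and without the last term.

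**1. Mediator.** Intubation risk is 0.60 with PDA/IVH and 0.25 without. The better schedule multiplies both by 0.8 (0.48 and 0.20).

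- PDA/IVH 50% against 25%: risks are 0.5×0.60 + 0.5×0.25 = 0.425 and 0.25×0.48 + 0.75×0.20 = 0.270.
- Unadjusted OR = (0.270/0.730)/(0.425/0.575) = 0.50.
- The ORs within PDA/IVH present and absent are 0.615 and 0.75; the adjusted fit gives 0.69.
- The risk difference standardised to the pooled PDA/IVH prevalence of 0.375 is −(0.375×0.12 + 0.625×0.05) = −0.076, against a total of −0.155.

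| PDA/IVH, two schedules | OR unadjusted → adjusted | Risk difference, points |
|---|---|---|
| 50% vs 25% | 0.50 → 0.69 | −15.5 → −7.6 |
| 40% vs 25% | 0.58 → 0.69 | −12.0 → −7.3 |
| 30% vs 25% | 0.67 → 0.70 | −8.5 → −6.9 |
| 30% vs 30% | 0.72 → 0.70 | −7.1 → −7.1 |

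The last row is the control. When schedule does not affect PDA/IVH, the risk difference does not move, and the small OR change is non-collapsibility only. If the whole effect runs through PDA/IVH (schedule OR 0.5 on PDA/IVH; PDA/IVH OR 2, 4 or 6 on intubation; baseline log-odds −1.4 and −1.1), true ORs of 0.94, 0.87 and 0.84 all become 1.00.

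**2. Common cause, no true effect on intubation.** Binary severity (50%) has an OR of 3 or 5 on both PDA/IVH and intubation. If schedule lowers PDA/IVH (OR 0.5 or 0.33), the intubation OR of 1.00 becomes about 1.04 to 1.12. If schedule raises it (OR 2 or 3), 1.00 becomes about 0.87 to 0.96.

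**3. Reverse order, no true effect on intubation.** Intubation risk is 0.25 in both groups, schedule has an OR of 0.5 on PDA/IVH, and intubation has an OR of 2, 4 or 6 on later PDA/IVH. The OR of 1.00 becomes 1.08, 1.20 and 1.28. If schedule reaches PDA/IVH only through intubation (OR 4), a true OR of 0.50 stays 0.50, although the standardised risk difference moves from −10.7 to −9.9 points.

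**Against sampling error.** The largest shift is ln(0.688/0.500) = 0.319. The standard error of the log OR at risks 0.425 and 0.270 is √[1/(n×0.425×0.575) + 1/(n×0.270×0.730)].

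- n = 60 per dose group: 0.391, so the shift is 0.82 SE.
- n = 30 per schedule: 0.553, so 0.58 SE.
- The amended ceiling of 220 less the 20 added for screen failures is 200, or 100 per dose group: 0.303, so 1.05 SE.

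**The case against.** The strongest defence is that this is a risk-factor model. The dependent variable is not named, the sentence follows a comparison of intubated and non-intubated infants, and schedule is one term among six. The first DMC recommendation asks for further factors associated with intubation and gives sepsis and NEC as examples, so postnatal morbidities were wanted as correlates. On that view the remedy is not to read the schedule coefficient causally, which is close to the plan's own caution. This has weight, and 72-hour intubation as the outcome is an inference, though the most natural one. But schedule stays in the model, and the neighbouring analysis also looks for modification by the intervention. Calling the analysis exploratory lowers the weight of a result; it does not tell the reader that the coefficient may no longer be the randomized effect.

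The sizes can also be challenged. Efficacy (1.1.7.4) attributes failure within 72 hours mainly to RDS, which argues against a strong PDA/IVH effect on early intubation. With a weak link (0.45 against 0.40, same factor 0.8), PDA/IVH of 50% against 25% moves the OR only from 0.67 to 0.70. All four schedules are active drug, and nothing in the documents shows that they differ in PDA or IVH. Both remarks stand, and they are why no size is claimed as an estimate.

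Finally, the study forms and mock tables (Appendices VIII and IX) are not available here and might fix the timing. The SAP text that can be read does not. By contrast, the DMC asked to "Control for mode of ventilation at baseline"; no such limit is attached to PDA or IVH.

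**Conclusion.** The concern holds. The plan uses PDA and IVH both as possible consequences of schedule and as adjustments for it, without a time limit, so the adjusted schedule effects can be biased in either direction. The likely size is modest. Across the assumed scenarios the largest shift is an OR of 0.50 becoming 0.69, under one standard error at 60 per dose group and about one at the amended maximum. The standardised risk difference is not distorted if schedule does not affect PDA/IVH and PDA/IVH does not follow intubation. The unadjusted test against 0.5, Tables 12 and 13, and the Aim #2 comparison stand as they are. This should be corrected, but it does not threaten the main results.

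**What to change.** In the adjusted-analyses sentence of 1.1.12, remove PDA and IVH from the covariates of any model that estimates schedule effects. Keep GA group, nebulizer type, mode of NIV at baseline (as the DMC asked) and antenatal steroids, and name the dependent variable. Report PDA and IVH as outcomes only.

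If their association with intubation is of interest, describe it separately, showing when each diagnosis was made relative to aerosolized surfactant and to intubation, and do not interpret a schedule coefficient from that description. Restricting the covariate to diagnoses made before the first aerosol dose would also remove the problem in principle, but with no baseline scan scheduled, deletion is cleaner.

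The cost is one line of SAP wording, with no new data and no change to sample size or power. The optional descriptive table needs diagnosis dates; the text available does not say whether these are recorded alongside the imaging results.
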